## **6. GENERAL ANALYSIS DEFINITIONS**

### **6.1 TREATMENTS**

For basic study information on investigational products and selection of doses, please see CTP Sections 3 and 4.

The study was performed as an open-label, two-treatment, two-period fixed sequence design trial in healthy male subjects in order to compare the test treatment (T) to the reference treatment (R). The treatments were one oral single dose of [REDACTED] BI 706321 administered as tablet formulation together with multiple oral doses of 200 mg itraconazole as oral solution formulation [REDACTED]

[REDACTED] BI 706321 as tablet given alone (R).

In total, it was planned to assign 14 healthy male subjects to the fixed sequence R-T.

There was a washout period of at least 14 days between the administrations of BI 706321.

For details of dosage and formulation see Table 6.1: 1 below:

Table 6.1: 1 Treatments and labels used in the analysis

Treatment	Short label
R BI 706321 [REDACTED] tablet, single dose	BI
T BI 706321 [REDACTED] tablet, single dose + Itraconazole 20 mL solution, 10 mg/mL, multiple dose	BI+ITZ

The following study phases will be defined for the analysis of AEs:

- **Screening**
  - Ranging from 0:00 h on day of informed consent until administration time of BI 706321 alone in treatment period 1.
- **On treatment** (labelled “BI”, “ITZ”, “BI+ITZ”)
  - **BI alone** (“BI”): Ranging from the time of administration of BI 706321 alone in treatment period 1 until 8 days (192 h) thereafter.
  - **Itraconazole alone** (“ITZ”): Ranging from the time of first administration of itraconazole until time of BI 706321 administration in treatment period 2 OR until 8 days (192 h) after the last administration of itraconazole, if subject discontinues treatment prior to administration of BI 706321.
  - **BI + ITZ** (“BI+ITZ”): Ranging from time of BI 706321 administration in treatment period 2 until 8 days (192 h) after the last administration of itraconazole OR 8 days (192 h) after the BI 706321 administration in treatment period 2, whatever occurs later.
- **Follow-up** (labelled “F/U BI”, “F/U ITZ”, “F/U BI+ITZ”)

- **F/U BI:** Ranging from the end of REP of BI 706321 in treatment period 1 until the first administration of itraconazole in period 2 or until trial termination, whatever occurs first.

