### Section 1.2.3 of CTP:

*The Residual Effect Period (REP, i.e., the period after the last dose with measurable drug levels and/or pharmacodynamic effects still likely to be present) of BI 706321 is assumed to be 8 days, [...].*

*For the use of itraconazole in Treatment T, the REP is defined as 8 days after last administration of itraconazole on Day 11 in Period 2.*

**Section 7.3.4 of the CTP:** *Note that AEs occurring after the last per protocol contact but entered before final database lock will be reported to Pharmacovigilance only and will not be captured in the trial database.*

The following AE displays will be provided in the report:

**A)** Section 15.3 and Appendix 16.1.13.1.8 (for ClinicalTrials.gov and EudraCT only) of the CTR displays:

In these displays, the on treatment phase will be analysed (labelled with the name of the study treatment (short label)). Screening and follow-up phases will not be included in this analysis.

The following totals will be provided in addition (Section 15.3 only):

- a total over all on treatment phase involving BI ("BI Total")
- a total over all on treatment phase included in this analysis ("Total")

**B)** Section 15.4 and Appendix 16.2.7 of the CTR displays:

- Screening
- On treatment (labelled with the name of the study treatment (short label))
- Follow-up BI (labelled "F/U BI")
- Follow-up BI+ITZ (labelled "F/U BI+ITZ")
- Follow-up ITZ (labelled "F/U ITZ") – if applicable

For detailed information on the handling of the treatments, refer to Technical TSAP ADS plan and Analysis Data Reviewers guide.

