Tabulations of frequencies for categorical data will include all possible categories available in the eCRF, and will display the number of observations in a category, as well as the percentage (%). Percentages will be rounded to one decimal place and will be based on all subjects in the respective subject set whether they have non-missing values or not. The category 'missing' will be displayed only if there are actually missing values.

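### The planned AE tables set a 192 h BI column beside a nominally 430 h BI+ITZ column as crude subject percentages; an equal-window companion table would be a cheap, low-priority improvement

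*SAP*

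**What the plan says.** SAP 6.1 defines three on-treatment phases for adverse events. BI alone is "Ranging from the time of administration of BI 706321 alone in treatment period 1 until 8 days (192 h) thereafter". ITZ alone runs from the first itraconazole dose to the BI 706321 dose in Period 2. BI+ITZ is "Ranging from time of BI 706321 administration in treatment period 2 until 8 days (192 h) after the last administration of itraconazole", with a floor of "8 days (192 h) after the BI 706321 administration in treatment period 2, whatever occurs later". The follow-up phase after BI alone is "Ranging from the end of REP of BI 706321 in treatment period 1 until the first administration of itraconazole in period 2".

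The same section assigns displays to phases. For "Section 15.3 and Appendix 16.1.13.1.8 (for ClinicalTrials.gov and EudraCT only) of the CTR displays", only on-treatment phases are used: "Screening and follow-up phases will not be included in this analysis". The only added columns, in Section 15.3, are totals over the phases involving BI and over all on-treatment phases. Section 15.4 and Appendix 16.2.7 also show screening and follow-up, as separate phases. Further detail is deferred: "For detailed information on the handling of the treatments, refer to Technical TSAP ADS plan and Analysis Data Reviewers guide".

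SAP 7.8.1 counts subjects with AEs, not events, and tabulates them by treatment. The general rule for categorical tables in SAP 7 is "Percentages will be rounded to one decimal place and will be based on all subjects in the respective subject set". No rate per unit of time is described.

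Protocol 7.3.4 plans a descriptive comparison of treatments and allows the SAP to define further intervals. Protocol 1.2.3 sets the residual effect period at 8 days for BI 706321, and at 8 days after the Day 11 dose for itraconazole.

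**The concern.** A percentage of subjects with at least one AE rises, or at best stays level, as the observation window lengthens. A reader who compares the BI and BI+ITZ columns of Section 15.3 will take a difference as a sign of what itraconazole adds, yet the second column nominally covers more than twice the time and has more scheduled questionings. The hours just after 192 h in Period 1 fall into follow-up and drop out of these tables, while the same post-dose hours in Period 2 are nominally counted.

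At stake is how the descriptive safety comparison reads, including in the registry displays. The PK endpoints are not affected, no hypothesis test of safety is planned, and no decision rule uses the T versus R difference in AEs.

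**Working it through.** **Inputs**
- BI phase: 8 days, stated as 192 h (SAP 6.1).
- BI 706321 dose: Day 1, 09:00. Last planned itraconazole dose: Day 11, 07:00, shown as 238:00. First itraconazole dose: -73:00 (Protocol Flow Chart, Period 2).
- At least 14 days between BI 706321 doses (Protocol 4.1.4).
- 14 subjects planned (Protocol 7.7).

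**Reproducing the plan's figures**
- 8 × 24 = 192 h, as stated.
- Day 1 09:00 to Day 11 07:00 = 10 × 24 − 2 = 238 h, as in the Flow Chart.

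**Window lengths**
- BI+ITZ = max(192, last itraconazole time + 192) = 238 + 192 = 430 h. This ends on Day 19 at 07:00, before the Day 25 to 35 end-of-trial visit, so that visit does not cut it short.
- Ratio 430/192 = 2.24.
- The 430 h is nominal. If the last itraconazole dose is at 142 h, the window is 334 h (1.74 times BI); if at 46 h, 238 h (1.24 times). It is never below 192 h.
- ITZ alone: 73 h.
- Follow-up after BI alone: at least 14 × 24 − 73 − 192 = 71 h, not shown in Section 15.3.

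**Scheduled post-dose AE questionings (Flow Chart)**
- BI: 4, 12, 24, 34, 46, 70, 94, 118, 142, 166 and 190 h = 11.
- BI+ITZ: 4, 12, 23, 28, 34, 46, 70, 94, 118, 142, 166, 190, 214, 238, 262, 310, 358 and 406 h = 18, of which 12 fall in the first 192 h.

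**Effect on a crude percentage**

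Assume complete follow-up and no itraconazole or period effect. Let *p* be the percentage with an AE in 192 h and *f* the share of the 430 h cumulative hazard that falls in the first 192 h. The 430 h percentage is then 1 − (1 − *p*)^(1/*f*). A constant hazard gives *f* = 192/430 = 0.447. Both *p* and *f* are assumptions.

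| Assumed *p* over 192 h | *f* = 1 | *f* = 0.8 | Constant hazard | Subjects of 14: 192 h vs 430 h, constant hazard |
|---|---|---|---|---|
| 10% | 10.0% | 12.3% | 21.0% | 1.4 vs 2.9 |
| 20% | 20.0% | 24.3% | 39.3% | 2.8 vs 5.5 |
| 40% | 40.0% | 47.2% | 68.1% | 5.6 vs 9.5 |

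Protocol 1.2.1 gives some context for *p*. In the first-in-human trial, treatment-emergent AEs occurred in 0 to 60% of subjects across BI 706321 dose groups and in 40% on placebo. A background AE rate is therefore plausible. The visible text does not say over what time those AEs were counted, so they fix neither *p* nor *f* here.

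**The case against.** The strongest reply is that the unequal windows are deliberate. Protocol 7.3.4 assigns AEs to treatment from intake to the end of the residual effect period. Treatment T is a course of itraconazole plus one BI 706321 dose, and Protocol 1.2.3 expects that exposure, and possibly adverse effects, may be prolonged under T. Events after 192 h can thus belong to T, and cutting at 192 h would drop the exposure the protocol flags. This stands as a defence of the phase definitions and the full-phase tables. It does not make crude percentages over 192 h and 430 h directly comparable.

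Second, nothing is hidden: the phase limits are stated, Section 15.4 shows follow-up after BI alone, and AE onset times are recorded (Protocol 5.2.6.2.1). This is also true, but a count rebuilt from listings is not a planned display.

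Third, further intervals are optional under Protocol 7.3.4, and the technical plan and internal AE display standards that the SAP cites were not available. So omitting an equal-window table breaks no commitment, and a reader should not infer that the sponsor has none. The point covers the visible text only.

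Fourth, equal hours do not give equal ascertainment. Within 192 h, safety laboratory draws fall at 24 and 142 h in R but at 46, 94 and 142 h in T, and the in-house stay is at least 24 h versus 46 h. This stands: the companion table would be closer to like-for-like, not fully so.

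**Conclusion.** The point holds as a low-priority improvement. In the visible SAP, the Section 15.3 and registry displays compare a 192 h window with a nominally 430 h window, and no equal-window view is specified. The 2.24 ratio assumes itraconazole is given through Day 11. The effect on percentages is unknown and can be zero; the constant-hazard figures show what is possible and are not an estimate of bias.

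A reader might infer two stronger things. One is that the phase definitions are wrong. They are not: they follow Protocol 1.2.3 and suit attribution. The other is that dropouts before Period 2 could reverse the direction, if the Period 2 percentage kept subjects never treated in that period in its denominator. The documents do not support building on that. The percentage rule in SAP 7 is a general one for categorical data, SAP 7.8.1 sends AE displays to standards not seen here, and nothing visible says the BI+ITZ column would be calculated that way.

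With about 14 subjects, a descriptive comparison and PK endpoints untouched, the practical consequence is small.

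**What to change.** Keep the full-phase tables for attribution. In SAP 6.1 and 7.8.1:

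- Add one companion Section 15.3 table of subjects with AEs starting 0 to 192 h after BI 706321 in each period, with the number treated in that period as denominator.
- Show BI+ITZ AEs starting after 192 h beside it, so that late events stay in view.
- Footnote the phase lengths: BI 192 h, ITZ nominally 73 h, BI+ITZ nominally 430 h.
- If the technical plan or display standards already contain such a table, cross-reference it instead.

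Do not substitute subjects with AEs per subject-day, which would rely on a constant hazard.

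The cost is one extra table and footnotes, from onset and dosing times already collected. Taken alone, the 0 to 192 h table omits late combination exposure, including the 214 h and 238 h itraconazole doses. It does not separate an interaction from itraconazole's own AEs or from period effects of the fixed sequence, and it only roughly equalises ascertainment. It therefore supplements the full-phase tables and does not replace them.

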### Section 1.2.3 of CTP:

*The Residual Effect Period (REP, i.e., the period after the last dose with measurable drug levels and/or pharmacodynamic effects still likely to be present) of BI 706321 is assumed to be 8 days, [...].*

*For the use of itraconazole in Treatment T, the REP is defined as 8 days after last administration of itraconazole on Day 11 in Period 2.*

**Section 7.3.4 of the CTP:** *Note that AEs occurring after the last per protocol contact but entered before final database lock will be reported to Pharmacovigilance only and will not be captured in the trial database.*

The following AE displays will be provided in the report:

**A)** Section 15.3 and Appendix 16.1.13.1.8 (for ClinicalTrials.gov and EudraCT only) of the CTR displays:

In these displays, the on treatment phase will be analysed (labelled with the name of the study treatment (short label)). Screening and follow-up phases will not be included in this analysis.

The following totals will be provided in addition (Section 15.3 only):

- a total over all on treatment phase involving BI ("BI Total")
- a total over all on treatment phase included in this analysis ("Total")

**B)** Section 15.4 and Appendix 16.2.7 of the CTR displays:

- Screening
- On treatment (labelled with the name of the study treatment (short label))
- Follow-up BI (labelled "F/U BI")
- Follow-up BI+ITZ (labelled "F/U BI+ITZ")
- Follow-up ITZ (labelled "F/U ITZ") – if applicable

For detailed information on the handling of the treatments, refer to Technical TSAP ADS plan and Analysis Data Reviewers guide.

## **6.2            IMPORTANT PROTOCOL DEVIATIONS**

Data discrepancies and deviations from the CTP will be identified for all treated subjects.

Consistency check listings (for identification of deviations of time windows) will be provided to be discussed at the Report Planning Meeting (RPM). At this meeting, all manual deviations identified at the sites by the Clinical Research Associates (CRAs) and deviations too complex to program will be reviewed by the trial team to decide which are considered important. For definition of important protocol deviations (iPD), and for the process of identification of these, refer to the Boehringer Ingelheim (BI) SOP "Identify and Manage Important Protocol Deviations (iPD)" [\(2\)](#).

Categories which are considered to be iPDs in this trial were suggested in the iPD specification file prior to trial initiation [\(3\)](#). IPDs will be identified no later than in the RPM, and the iPD categories in the iPD specification file will be updated as needed. If any iPDs are identified, they are to be summarised into categories and will be captured in the RPM minutes (the decision log) and in the iPD specification file. The decision on exclusion of subjects from analysis sets will be made after discussion of exceptional cases and implications for analyses.

The iPDs will be summarised and listed.

## 6.3 SUBJECT SETS ANALYSED

### Section 7.3 of the CTP:

- *Treated set (TS): The treated set includes all subjects who were treated with at least one dose of study drug. The treated set will be used for safety analyses.*
- *Pharmacokinetic parameter analysis set (PKS): This set includes all subjects in the treated set (TS) who provide at least one PK endpoint that was defined as primary or secondary and was not excluded due to a protocol deviation relevant to the evaluation of PK or due to PK non-evaluability (as specified in the following subsection 'Pharmacokinetics'). Thus, a subject will be included in the PKS, even if he contributes only one PK parameter value for one period to the statistical assessment. Descriptive and model based analyses of PK parameters will be based on the PKS.*

[...]

*Plasma concentration data and parameters of a subject will be included in the statistical pharmacokinetic (PK) analyses if they are not flagged for exclusion due to a protocol deviation relevant to the evaluation of PK (to be decided no later than in the Report Planning Meeting) or due to PK non-evaluability (as revealed during data analysis, based on the criteria specified below). Exclusion of a subject's data will be documented in the CTR.*

*Relevant protocol deviations may be:*

- *Incorrect trial medication taken, i.e. the subject received at least one dose of trial medication the subject was not assigned to*
- *Incorrect dose of trial medication taken*
- *Use of restricted medications*

[figure not shown]
*Plasma concentrations and/or parameters of a subject will be considered as non-evaluatable, if for example*

- *The subject experienced emesis that occurred at or before two times median  $t_{max}$  of the respective treatment (median  $t_{max}$  is to be determined excluding the subjects experiencing emesis)*
- *A predose concentration of BI 706321 is >5%  $C_{max}$  value of that subject in the respective treatment period*
- *Missing samples/concentration data at important phases of PK disposition curve*

The descriptive analysis of PK concentrations will be based on the ADS ADPC as described at the beginning of [Section 7](#).

Table 6.3: 1 Subject sets analysed

Class of endpoint	Subject set	
	TS	PKS
Analyses of PK endpoints		X
Safety parameters	X	
Demographic/baseline parameters	X	
Important protocol deviations	X	
Disposition	X	
Exposure	X	

## **6.5 POOLING OF CENTRES**

This section is not applicable, because the study was performed in only one centre.

## **6.6 HANDLING OF MISSING DATA AND OUTLIERS**

Handling of missing data and outliers will be performed as described in the CTP, Section 7.5.

The only exceptions where imputation might be necessary for safety evaluation are AE dates. Missing or incomplete AE dates are imputed according to BI standards (see BI-KMED-BDS-HTG-0035) (4).

Missing data and outliers of PK data are handled according to BI standards (see BI-KMED-TMCP-MAN-0012 (5) and BI-KMED-TMCP-MAN-0014 (6)).

## **6.7 BASELINE, TIME WINDOWS AND CALCULATED VISITS**

The baseline value is defined as the last measurement before administration of BI 706321 in each treatment period.

For laboratory analysis the baseline of first period is defined as last measurement before administration of BI 706321 (i.e. day 1, ptm -73:00h), and the baseline of second period is defined as last measurement before administration of first itraconazole dose (i.e. day -3, ptm -73:00h).

**Section 6.1 of the CTP:** *Exact times of measurements outside the permitted time windows will be documented. The acceptable time windows for screening, the end of trial examination,*

*and measurements and assessments scheduled to occur 'before' trial medication administrations are provided in the CTP Flow Chart.*

*If not stated otherwise in the Flow chart, the acceptable deviation from the scheduled time for the assessment of safety (e.g. vital signs, ECG, laboratory tests) will be  $\pm 30$  min.*

Adherence to time windows will be checked via the consistency check listings at the RPM.

Unscheduled measurements of laboratory data and vital signs data will be assumed to be repeat measurements of the most recent scheduled measurement (e.g. for follow-up or confirmation of a particular value). Therefore, unscheduled measurements will be assigned to the planned time point of the previous scheduled measurement.

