Proprietary confidential information © 2021 Boehringer Ingelheim International GmbH or one or more of its affiliated companies

FLOW CHART (cont'd)

Period	Visit	Day	Planned time (relative to drug administration) [h:min]	Approximate clock time of actual day [h:min]	Event and comment	Safety laboratory ⁵	PK blood, BI 706321	12-lead ECG	Vital signs (body temperature BP, PR)	Questioning for AEs and concomitant therapy ⁷
Period 2/ Treatment T (BI 706321 + itraconazole) ⁸	3	-3	-73:00	08:00	Ambulatory visit, itraconazole administration	x ^{B,2,3}				x ²
		-2	-49:00	08:00	Ambulatory visit, itraconazole administration					x ²
		-1	-25:00	08:00	Ambulatory visit, itraconazole administration	x ^{C,2}				x ²
	1	-3:00	06:00		Admission to trial site ²			x ²	x ²	x ²
		-1:00	08:00		Itraconazole administration		x ²			
		0:00	09:00		BI 706321 administration					
		0:30	09:30			x				
		1:00	10:00			x				
		2:00	11:00		240 mL fluid intake	x				
		3:00	12:00			x				
		4:00	13:00		240 mL fluid intake, thereafter lunch ⁴	x		x	x	x
		5:00	14:00			x				
		6:00	15:00			x				
		7:00	16:00		Snack (voluntary) ⁴	x				
		8:00	17:00			x				
		10:00	19:00		Dinner ⁴	x				
		12:00	21:00			x				x
	2	23:00	08:00		Itraconazole administration					x ²
		24:00	09:00		Breakfast ⁴		x			
		28:00	13:00		Lunch ⁴					x
		31:00	16:00		Snack (voluntary) ⁴					
		34:00	19:00		Dinner ⁴	x				x
	3	46:00	07:00		Itraconazole administration, discharge from trial site	x ^{B,2}	x ⁹	x ²	x ²	x ²
	4	70:00	07:00		Ambulatory visit, itraconazole administration		x ⁹			x ²
	5	94:00	07:00		Ambulatory visit, itraconazole administration	x ^{C,2}	x ⁹			x ²
	6	118:00	07:00		Ambulatory visit, itraconazole administration		x ⁹			x ²
	7	142:00	07:00		Ambulatory visit, itraconazole administration	x ^{B,2}	x ⁹			x ²
	8	166:00	07:00		Ambulatory visit, itraconazole administration		x ⁹			x ²
	9	190:00	07:00		Ambulatory visit, itraconazole administration		x ⁹			x ²
	10	214:00	07:00		Ambulatory visit, itraconazole administration	x ^{C,2}	x ⁹			x ²
	11	238:00	07:00		Ambulatory visit, itraconazole administration					x ²
	12	262:00	07:00		Ambulatory visit		x			x
	14	310:00	07:00		Ambulatory visit	x ^C	x			x
	16	358:00	07:00		Ambulatory visit		x			x
	18	406:00	07:00		Ambulatory visit		x			x
	20	454:00	07:00		Ambulatory visit		x			x
	22	502:00	07:00		Ambulatory visit		x			x
	24	550:00	07:00		Ambulatory visit		x			x
FU	4	25 to 35			End of trial (EoTrial) examination ⁶	x ^D		x	x	x

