1.2.3 Residual Effect Period

The Residual Effect Period (REP, i.e., the period after the last dose with measurable drug levels and/or pharmacodynamic effects still likely to be present) of BI 706321 is assumed to be 8 days, i.e. based on [redacted] terminal $t_{1/2}$ seen in the FIH trial 1425-0001.

When given together with itraconazole (Treatment T), it is expected that plasma exposure of BI 706321 could be increased (albeit within the exposures explored in the clinical trial 1425-0001), and the time of relevant plasma exposure could be prolonged. This might result in a prolonged period in which adverse effects could potentially occur.

For the use of itraconazole in Treatment T, the REP is defined as 8 days after last administration of itraconazole on Day 11 in Period 2.

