3. DESCRIPTION OF DESIGN AND TRIAL POPULATION

3.1 OVERALL TRIAL DESIGN AND PLAN

The study will be performed as an open-label, two-treatment, two-period, fixed sequence design trial in healthy male subjects in order to compare the test treatment (T) to the reference treatment (R). The treatments will be one oral single dose of [REDACTED] BI 706321 administered as tablet formulation together with multiple oral doses of 200 mg itraconazole as oral solution formulation (concentration: 10 mg/mL) (treatment T) and one single dose of [REDACTED] BI 706321 as tablet given alone (R).

In both treatments, BI 706321 is administered to subjects in the fasting state. In the first treatment period (Period 1, Visit 2), all subjects are planned to undergo treatment R, and in the second treatment period (Period 2, Visit 3), all subjects are planned to undergo treatment T. For details, refer to Section [4.1](#).

There will be a washout period of at least 14 days between the administrations of BI 706321.

[figure not shown]

Figure 3.1: 1

Trial design

An overview of all relevant trial activities is provided in the [Flow Chart](#). For visit schedule and details of trial procedures at selected visits, refer to Sections [6.1](#) and [6.2](#), respectively.

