5.2.6.1.4 Adverse events of special interest

The term adverse events of special interest (AESI) relates to any specific AE that has been identified at the project level as being of particular concern for prospective safety monitoring and safety assessment within this trial, e.g. the potential for AEs based on knowledge from other compounds in the same class. AESIs need to be reported to the sponsor's Pharmacovigilance Department within the same timeframe that applies to SAEs, please see Section [5.2.6.2.2](#).

The following are considered as AESIs:

- Hepatic injury
A hepatic injury is defined by the following alterations of hepatic laboratory parameters:
 - o An elevation of AST (aspartate transaminase) and/or ALT (alanine transaminase) ≥ 3 -fold ULN combined with an elevation of total bilirubin ≥ 2 -fold ULN measured in the same blood sample, or
 - o Aminotransferase (ALT, and/or AST) elevations ≥ 10 fold ULN

These lab findings constitute a hepatic injury alert and the subjects showing these lab abnormalities need to be followed up according to the 'DILI checklist' provided in the ISF. In case of clinical symptoms of hepatic injury (icterus, unexplained encephalopathy, unexplained coagulopathy, right upper quadrant abdominal pain, etc.) without lab results (ALT, AST, total bilirubin) available, the Investigator should make sure that these parameters are analysed, if necessary in an unscheduled blood test. Should the results meet the criteria of hepatic injury alert, the procedures described in the DILI checklist should be followed.

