7.3.4 Safety analyses

Safety will be analysed based on the assessments described in Section 2.2.2.2. All treated subjects (TS, refer to Section 7.2) will be included in the safety analysis. Safety analyses will be descriptive in nature and based on BI standards. No hypothesis testing is planned.

Proprietary confidential information © 2021 Boehringer Ingelheim International GmbH or one or more of its affiliated companies

For all analyses, the treatment actually administered (= treatment at onset) to the subject will be used (any deviations from treatment will be discussed in the minutes of the Report Planning Meeting).

Treatments will be compared in a descriptive way. Tabulations of frequencies/proportions will be used to evaluate categorical (qualitative) data, and tabulations of descriptive statistics will be used to analyse continuous (quantitative) data.

Measurements (such as ECG, vital signs, or laboratory parameters) or AEs will be assigned to treatments (see Section [4.1](#)) based on the actual treatment at the planned time of the measurement or on the recorded time of AE onset (concept of treatment emergent AEs). Therefore, measurements planned or AEs recorded prior to first intake of trial medication will be assigned to the screening period, those between first trial medication intake and end of REP (see Section [1.2.3](#)) will be assigned to the treatment period. Events occurring after the REP but prior to next intake or end of trial termination date will be assigned to 'follow-up'. In case of two or more treatments, the follow-up will be summarized according to the previous treatment. These assignments including the corresponding time intervals will be defined in detail in the TSAP. Note that AEs occurring after the last per protocol contact but entered before final database lock will be reported to Pharmacovigilance only and will not be captured in the trial database.

Additionally, further treatment intervals (analysing treatments) may be defined in the TSAP in order to provide summary statistics for time intervals, such as combined treatments, on-treatment totals, or periods without treatment effects (such as screening and follow-up intervals).

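### SAP 6.7 files an unscheduled on-drug lab or vital-sign value in a pre-dose row if it comes before the next scheduled on-drug measurement (minor)

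*SAP*

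**What the plan says.** SAP 6.7 holds that unscheduled laboratory and vital-sign values are "assumed to be repeat measurements of the most recent scheduled measurement" and draws the consequence: "Therefore, unscheduled measurements will be assigned to the planned time point of the previous scheduled measurement". No exception is stated for a dose given in between or for a change of period.

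Three other rules make the planned time matter:

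- SAP 7.8.2 summarises laboratory data by planned time, using each subject's worst value at that time or assigned to it.
- SAP 7.8.3 does the same for vital signs, using the last value.
- Protocol 7.3.4 attributes measurements and AEs "based on the actual treatment at the planned time of the measurement or on the recorded time of AE onset", and adds that "measurements planned or AEs recorded prior to first intake of trial medication will be assigned to the screening period". It leaves the detailed intervals to the SAP, but SAP 6.1 defines phases for AEs only.

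SAP 6.7 also defines baseline. In general it is the last measurement before BI 706321 in each period. For laboratory data in Period 2 it is the last measurement before the first itraconazole dose. Both laboratory baselines are also labelled with planned time -73:00.

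**The concern.** The repeat assumption suits a confirmatory retest. It does not suit a value prompted by something new, and the protocol foresees at least one such case. If signs of hepatic injury appear and no liver results are at hand, "the Investigator should make sure that these parameters are analysed, if necessary in an unscheduled blood test" (Protocol 5.2.6.1.4). A test of that kind drawn after dosing is not a repeat of the pre-dose sample, yet SAP 6.7 files it there.

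The two summary rules then act differently. A misfiled laboratory value displaces the true pre-dose value in the row if it is worse. A misfiled vital sign displaces it in any case, because it is later. The reader of the by-time table would see an on-drug value as pre-dose, and planned-time attribution would give it the wrong label as well.

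**Working it through.** **Inputs.** Scheduled times are in hours relative to BI 706321, from the Protocol Flow Chart. The contents of laboratory sets B and C are from Protocol Table 5.2.3: 1.

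- Period 1 labs (set B): -73, 24, 142.
- Period 1 vital signs, legible cells: -3, 4, 24.
- Period 2 labs: set B at -73, 46, 142; set C at -25, 94, 214, 310. Set C holds only AST, ALT, alkaline phosphatase, GGT and bilirubin, all of which are also in set B.
- Period 2 vital signs: -3, 4, 46.
- Period 2 itraconazole: first dose at -73, after the pre-dose sample; then -49, -25, -1 and onward.

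**Rule applied.** Row for a value taken at time t = the latest scheduled time not later than t, for that test.

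| Value taken | Filed at | Window length | What the row represents |
|---|---|---|---|
| Period 1 labs, 0 to 24 h | -73:00 | 24 - 0 = 24 h | before any trial drug (screening by Protocol 7.3.4) |
| Period 1 vital signs, 0 to 4 h | -3:00 | 4 - 0 = 4 h | before any trial drug (screening by Protocol 7.3.4) |
| Period 2 liver tests and bilirubin, -73 to -25 h | -73:00 | 73 - 25 = 48 h | before itraconazole |
| Period 2 tests in set B but not C, -73 to 46 h | -73:00 | 73 + 46 = 119 h, of which 46 h after BI 706321 | before itraconazole |
| Period 2 liver tests and bilirubin, 0 to 46 h | -25:00 | 46 h | before BI 706321, itraconazole already started |
| Period 2 vital signs, 0 to 4 h | -3:00 | 4 h | before BI 706321, itraconazole already started |

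The fourth line covers haematology, creatinine, creatine kinase and electrolytes, among others. They have no draw between -73:00 and 46:00, so a value taken almost two days after BI 706321 can still land in the pre-itraconazole row.

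**Is the Period 2 -73:00 row really off drug?** Protocol 3.1 says: "There will be a washout period of at least 14 days between the administrations of BI 706321". At that minimum of 14 × 24 = 336 h, the row lies 336 - 73 = 263 h after the Period 1 dose. The residual effect period "of BI 706321 is assumed to be 8 days" (Protocol 1.2.3), or 192 h. The row is therefore 263 - 192 = 71 h past it. By the plan's own definitions it is a drug-free row.

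**Size, on assumed values.** The documents give neither frequency nor values for unscheduled measurements, so these are illustrations for one subject. Shift in row mean = (misfiled value - true value) / number of subjects.

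- ALT 30 U/L at Period 2 -73:00, unscheduled 90 on Day -2: 60/14 = 4.3 U/L. For unscheduled values of 60 to 120, the range is 30/14 = 2.1 to 90/14 = 6.4. With 12 subjects: 60/12 = 5.0 (30/12 = 2.5 to 90/12 = 7.5).
- Systolic pressure 20 mmHg below the Period 1 -3:00 value, taken 0 to 4 h after dosing: 20/14 = 1.4 mmHg. For differences of 10 to 40, the range is 10/14 = 0.7 to 40/14 = 2.9. With 12 subjects: 20/12 = 1.7 (10/12 = 0.8 to 40/12 = 3.3).

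**The case against.** The case for leaving the text alone has four parts.

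- **Little is at stake.** Safety analysis is descriptive, individual values are listed, out-of-range labs are flagged, and clinically relevant findings become AEs, which are assigned by recorded onset. This stands and limits the severity. It does not make the table row right.
- **Most unscheduled values will be retests.** Protocol 5.2.3 mentions retests, and the symptom-driven blood test in 5.2.6.1.4 is a narrow case. No passage specifically foresees symptom-driven vital signs. This stands as to likelihood. The rule nevertheless covers all unscheduled values, including the kind the protocol foresees.
- **The handling may be specified elsewhere.** SAP 6.1 points to a technical ADS plan and a data reviewers' guide, and SAP 7.8.2 to a company laboratory standard. These may contain a carve-out and were not available. The SAP itself states none.
- **Actual-time attribution departs from Protocol 7.3.4.** That is true, and the fix should say so openly.

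A reader might also infer that Period 2 vital signs taken before -3:00 are filed under Period 1, BI 706321 alone. Period 2 schedules none before -3:00, so a strictly literal search goes back across the wash-out. The documents do not settle this: a within-period reading is possible, and Period 1 cells are partly redacted. It is a secondary point only.

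**Conclusion.** The concern holds as a minor defect. Followed as written, SAP 6.7 puts an on-drug value in a pre-dose row if that value is unscheduled and precedes the next scheduled on-drug measurement of the same test. The nominal windows run from 4 h to 119 h. The longest applies to Period 2 tests in set B but not C. The Period 1 vital-sign window rests on the legible Flow Chart cells.

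Three stronger readings are not supported:

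- Not every unscheduled on-drug value is misplaced. Once a scheduled on-drug measurement has been taken, later unscheduled values go to on-drug rows.
- Baseline is not corrupted by the text. Its definition requires a measurement before administration, which excludes post-dose values. The -73:00 label should not override that, and the SAP would do well to say so.
- The trial's conclusions on exposure are not touched. PK endpoints, AE and AESI tables, laboratory flags and listings are unaffected, as are scheduled post-dose values in their own rows.

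There is also one plain inconsistency, independent of any unscheduled value. SAP 6.7 places the Period 1 laboratory baseline on Day 1 at -73:00, while the Flow Chart has -73:00 at Day -3 to -1.

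**What to change.** In SAP 6.7:

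1. Keep the repeat rule. Add that an unscheduled value taken after the first itraconazole dose, or after BI 706321, is not assigned to a planned time before that intake or in an earlier period. Attribute it by actual date and time and show it as a separate unscheduled category.
2. State that baseline is selected by actual date and time before any reassignment.
3. Reconcile the Day 1 label for -73:00 with the Flow Chart.

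In SAP section 4, which at present declares no changes, record item 1 as a clarification of the planned-time rule in Protocol 7.3.4.

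The cost is one derivation condition, one table category and no new data. The drawback is that a confirmatory retest drawn after dosing will be shown apart from the sample it confirms. This can happen because Flow Chart footnote 2 places pre-dose procedures within 3 h before dosing. A cross-reference in the listing deals with it.
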